5.5 Determination of missing adequate assessments

The term ‘missing adequate assessment’ refers to assessments that are not done or for which the overall lesion response is ‘NE’. ‘Missing adequate assessment’ will also be referred to as ‘missing assessment’.

The PFS censoring and event date options depend on the presence and the number of missing tumor assessments.

An exact rule to determine whether there are no, one or two missing TAs is therefore needed. This rule is based on the interval between the last adequate tumor assessment (LATA) date and the event date. The scheduled date of tumor assessments (in weeks from randomization), protocol specified window for tumor assessments, and the thresholds for LATA that belong to a visit can be found in [Table 5.5-1](#) below.

Table 5.5-1 Schedule for tumor assessment and time windows

Assessment schedule	Schedule week – 1 week	Schedule week (weeks from randomization)	Schedule week + 1 week	Threshold (weeks)*
Baseline	N/A	N/A	N/A	N/A
Week 16	15	16	17	20
Week 24	23	24	23	28
Week 36	35	36	37	42
Week 48	47	48	49	54
Week 60	59	60	61	66
Week 72	71	72	73	78
Week 72+12x**	71+12x	72+12x	73+12x	78+12x

* The mid-point between current and next visit (except for baseline) and the upper limit for LATA to be matched to a certain scheduled assessment, e.g., if LATA is at Week 21, this is after the threshold for Week 16, and before that for Week 24, so the matching scheduled assessment is Week 24.

** For all scheduled assessments after week 72, such as Week 84 (x = 1), Week 96 (x = 2), etc...

To calculate the number of missing tumor assessments, the LATA before an event is matched with a scheduled tumor assessment using the time window in the table above (essentially whichever scheduled assessment it is closest to). Two thresholds, D1 and D2 are calculated for that scheduled assessment based on the protocol-specified scheduled and windows:

- An event after LATA+D1 will be considered as having ≥ 1 missing assessment
- An event after LATA+D2 will be considered as having ≥ 2 missing assessments

Since there is a change of schedule for tumor assessments at Week 16 and Week 24, D1 and D2 are defined differently depending on when LATA happens.

Rule 1: if LATA happens before Week 16 (if LATA is at baseline, then LATA starts at Day 1)

- $D1 = 16 \text{ weeks} + 14 \text{ days} = 126 \text{ days}$
- $D2 = 16 \text{ weeks} + 8 \text{ weeks} + 14 \text{ days} = 182 \text{ days}$

Rule 2: if LATA occurs between Week 16 and Week 24

- $D1 = 8 \text{ weeks} + 14 \text{ days} = 70 \text{ days}$
- $D2 = 8 \text{ weeks} + 12 \text{ weeks} + 14 \text{ days} = 154 \text{ days}$

Rule 3: if LATA occurs from Week 24 onward

- $D1 = 12 \text{ weeks} + 14 \text{ days} = 98 \text{ days}$
- $D2 = 12 \text{ weeks} + 12 \text{ weeks} + 14 \text{ days} = 182 \text{ days}$

The date of next scheduled assessment is defined as the date of the late adequate tumor assessment plus the protocol specified time interval for assessments. The protocol specified time interval for tumor assessments is captured in the above table (± 1 week).

6 References

2. Armitage P, McPherson CK and Rowe BC (1969). Repeated significance tests on accumulating data. *J.R. Statist. Soc. A*, 132, 232-244.
4. Brookmeyer R and Crowley J (1982). A Confidence Interval for the Median Survival Time. *Biometrics*, 38, 29 - 41.
5. Clopper CJ and Pearson ES (1934). The use of confidence or fiducial limits illustrated in the case of the binomial. *Biometrical*, 26, 404-413.
6. Collet D (1994). Modelling survival data in medical research. London, Chapman & Hall.
8. FDA briefing Document Oncologic Drugs Advisory Committee Meeting, July 24, 2012, Evaluation of radiologic review of progression-free survival in Non-hematologic malignancies.
<http://www.fda.gov/downloads/advisorycommittees/committeesmeetingmaterials/drugs/oncologicdrugsadvisorycommittee/ucm311141.pdf>
9. Fleming TR, Harrington DP and O'Brien PC (1984). Designs for group sequential tests. *Controlled Clinical Trials*, 5, 348-361.
10. Greenland S, Lanes S and Jara M (2008). Estimating effects from randomized trials with discontinuations: the need for intent-to-treat design and G-estimation. *Clinical Trials*, 5, 5-13.

11. Glimm E, Maurer W and Bretz F (2010). Hierarchical testing of multiple endpoints in group-sequential trials. *Statistics in Medicine*, 29, 219-228.

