8.3 Efficacy Assessment

8.3.1 Progression Free Survival

The primary efficacy end-point is PFS as measured by objective tumor response, which is determined by RECIST criteria, Version 1.1 (Eisenhauer, et al., 2009). Tumor response will be assessed locally and centrally.

Triphasic CT imaging is the preferred modality over MRI for determining objective tumor response. Combined PET/CT may be used only if the CT is of similar diagnostic quality as a CT performed without PET, including the utilization of IV contrast media.

The baseline CT/MRI scan should be taken possibly on the same day of randomization or immediately before (within 1 week) to ensure that it reflects the disease status closely before the therapy start. The results of baseline CT/MRI must be assessed by the Investigator before randomization.

The tumor diameters of indicator lesions used for response assessment should be measured in the closest position to that used for the baseline CT or MRI assessment.

Restaging is scheduled at regular intervals in the two treatment arms (week 16 ± 1 , week 24 ± 1 and then every 12 ± 1 weeks) starting from the date of randomization (see Table 8-3, and Table 8-4). Every effort should be done to avoid differences between these timings for patients in the two arms. In case of delays, the reason of the delay has to be documented and the CT/MRI assessment has to be done as soon as possible.

If a CT/MRI scan is done on the same day of a Lutathera administration (e.g. in case of therapy postponement due to DMT or scheduling issues), the scan should be taken before the drug administration. When a CT/MRI assessment is >6 weeks earlier or later than the original schedule, the next reassessments have to be discussed and adjusted with the Medical Monitor of the study in a way to progressively come back to the original schedule.

It is recommended that for each patient identical acquisition and reconstruction protocols be used at all time-points. Central, blinded, real-time IRC (Independent Review Committee) assessment will be conducted for determining progressive disease. Changes from randomization date will be assessed at week 16 ± 1 , week 24 ± 1 and then every 12 ± 1 weeks until the PFS primary analysis End-Point has been reached, then until Week 72 after randomization, unless the patient progresses or dies.

Sponsor will notify all the Centers and their Ethic Committees as soon as the 99 PFS events have occurred.

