2.5.4 Handling of missing values/censoring/discontinuations

This is an event-driven trial and the primary analysis for PFS will be performed after 99 PFS events have been documented based on central review of tumor assessments.

In the primary analysis, PFS will be censored at the date of the last adequate tumor assessment if no PFS event is observed prior to the analysis cut-off date.

Disease progressions (i.e., central review RECIST 1.1 documented disease progression) or deaths documented after the initiation of new anti-cancer therapy will not be counted as PFS events for the primary analysis.

The date of last adequate tumor assessment is the date of the last tumor assessment with overall response of CR, PR, or SD before an event or a censoring reason occurred. In this case, the last tumor evaluation date at that assessment will be used. If no post-baseline assessments are available (before an event or a censoring reason occurred) then the date of randomization will be used.

In particular, PFS will be censored at the last adequate tumor assessment if one of the following occurs: absence of event; the event occurred after two or more missing tumor assessments.

The term “missing adequate tumor assessment” is defined as a tumor assessment not performed or tumor assessment with overall response of “UNK”. The rule to determine number of missing tumor assessments is based on the time interval between the date of last adequate tumor assessment and the date of an event. If the interval is greater than twice the protocol-specified interval between the tumor assessments and 2 times the protocol-allowed time window around assessments, then the number of missing assessments will be 2 or more.

Note that according to the protocol the first tumor assessment should occur at 16 weeks, then the second tumor assessment should occur 8 weeks later, and then the frequency should be every 12 weeks thereafter. For patients who discontinue from treatment without PD due to central review, tumor assessments should be taken every 12 weeks starting from the last tumor assessment until documented disease progression for central review per RECIST 1.1. Exact time windows to take into account missing assessments for PFS event determination is further discussed in [Section 5.5](#).

Refer to [Table 2.5-1](#) for censoring and event date options and outcomes for primary PFS.

Table 2.5-1 Derivation of primary PFS

Situation	Options	Outcome

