A. No baseline assessment, or, No post baseline assessment	Date of randomization	Censored
B. Progression or death at or before next scheduled assessment	Date of progression (or death)	Progressed
C. Progression or death after exactly one missing assessment	Date of progression (or death)	Progressed
D. Progression or death after two or more missing assessments	Date of last adequate assessment prior to missed assessment	Censored
E. No progression (or death)	Date of last adequate assessment	Censored
F. Treatment discontinuation due to 'Disease progression' without documented progression, i.e., clinical progression based on investigator claim	Ignore clinical progression and follow situations above	As per above situations
G. Start of new anticancer therapy, cross-over to or re-treatment with Lutathera prior to protocol defined progression per central review	Primary analysis: Censor patient at last adequate tumor assessment prior to new anti-cancer therapy	Censored
H. Death before first PD assessment	Date of death	Event

In particular, for censoring reason G in [Table 2.5-1](#), new anticancer therapy is defined as one of the following:

- For new anti-cancer medications post-randomization:
 - Medications which are in the ATC2 class of Antineoplastic agents or
 - Medications which are in the ATC4 class of Various therapeutic radiopharmaceuticals

- Class of medications of Somatostatin and Analogues excluding Octreotide and Octreotide Acetate
- For new anti-cancer procedures post randomization:
 - Any radiotherapies
 - Procedures (including surgery) with indication of Underlying disease in Concomitant non-drug therapies and interventions eCRF page

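### SAP 5.5 gives two conflicting criteria for choosing the missed-scan limits, so an in-window early Week 24 scan can turn a primary PFS event into a censored observation, depending on which the programmer follows

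*SAP*

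**What the plan says.** Protocol 8.3.1 schedules scans at week 16 ± 1, "week 24 ± 1 and then every 12 ± 1 weeks", counted from randomization. SAP 2.5.4 restates this: "the first tumor assessment should occur at 16 weeks, then the second tumor assessment should occur 8 weeks later", then every 12 weeks.

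SAP 5.5 counts missed scans from the interval between the last adequate tumor assessment (LATA) and the event. An event later than LATA + D1 has at least one missing scan; an event later than LATA + D2 has at least two. Table 2.5-1 in SAP 2.5.4 then sets the outcome. Row "C. Progression or death after exactly one missing assessment" is an event on its own date; row D, for two or more, is censored at the last adequate assessment.

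Section 5.5 chooses D1 and D2 in two ways:

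- **By matched visit.** The LATA is first matched to the nearest scheduled visit, and D1 and D2 are said to be computed for that visit. The table footnote gives a worked case: a LATA at week 21 is matched to Week 24.
- **By timing of the LATA.** The next paragraph says "D1 and D2 are defined differently depending on when LATA happens", and the rules follow: "Rule 1: if LATA happens before Week 16" (126 and 182 days), "Rule 2: if LATA occurs between Week 16 and Week 24" (70 and 154 days) and "Rule 3: if LATA occurs from Week 24 onward" (98 and 182 days).

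Table 5.5-1 also gives each visit's window and a threshold, defined as "The mid-point between current and next visit (except for baseline) and the upper limit for LATA to be matched to a certain scheduled assessment". The Week 24 row reads 23 / 24 / 23 / 28.

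**The concern.** The two criteria disagree for patients scanned exactly as the protocol allows. A Week 24 scan taken up to seven days early matches the Week 24 visit, but its date lies between Week 16 and Week 24. The SAP's own week 21 example has the same conflict: it is matched to Week 24, yet by date it falls under Rule 2. Rule 2's limits are built from the gaps that follow a Week 16 scan (8 weeks, then 12), whereas the gaps after a Week 24 scan are 12 and 12.

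At stake is event or censored status in the primary endpoint. The same count feeds the backdating supplementary analysis and the summary of censoring reasons (SAP 2.5.6), and duration of response, which borrows the Table 2.5-1 rules (SAP 2.7.1).

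**Working it through.** Days below are days elapsed since randomization (7 × week).

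**1. The stated limits reproduce.** Each is 7 × the scheduled gap or gaps, plus 14 days.

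| Rule | D1 | D2 |
|---|---|---|
| 1 | 16×7 + 14 = 126 | 24×7 + 14 = 182 |
| 2 | 8×7 + 14 = 70 | 20×7 + 14 = 154 |
| 3 | 12×7 + 14 = 98 | 24×7 + 14 = 182 |

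All six agree with the SAP. The general two-missing rule in SAP 2.5.4, applied to the 12-weekly schedule, gives 2×12 + 2×1 = 26 weeks = 182 days, which is Rule 3's D2.

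**2. Windows.** Week 24 ± 1 is days 161–175, of which 161–167 precede day 168. Week 36 ± 1 is days 245–259. Week 48 ± 1 is days 329–343.

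**3. Only Week 36 missed, progression at the Week 48 scan, LATA on days 161–167.** The interval runs from 329 − 167 = 162 to 343 − 161 = 182 days. There are 7 × 15 = 105 combinations of LATA day and event day.

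- Literal rule (D2 = 154): 105 of 105 censored.
- Matched visit (D2 = 182): 0 of 105 censored.

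For example, with LATA on day 161 and progression on day 336, the interval is 175 days: above 154, within 182. With LATA on days 168–175, Rule 3 applies either way and 0 of 120 are censored.

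**4. No scan missed, progression at the Week 36 scan, LATA on days 161–167.** The interval runs from 245 − 167 = 78 to 259 − 161 = 98 days. The literal D1 of 70 flags a missing scan in 105 of 105; the matched D1 of 98 flags none. The backdating analysis would then re-date these events to LATA + 84 days, that is days 245–251, moving an event back by at most 259 − 245 = 14 days.

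**5. Week 16 scans on days 105–111.** By date these get Rule 1 rather than Rule 2. Intervals to the Week 24, 36 and 48 windows are 50–70, 134–154 and 218–238 days, and both rules give the same missing count for each. Only off-schedule events can differ; for censoring, these are events at about weeks 37 to 42.

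**6. Week 24 row of Table 5.5-1.** 24 + 1 = 25, not 23. The mid-point of 24 and 36 is 30, not 28. The other rows follow the mid-point definition (20, 42, 54, 66, 78). A LATA at weeks 28 to 30 gets Rule 3 whether matched to Week 24 or Week 36, so this row correction changes no D1 or D2.

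**7. Size.** From SAP section 3: 74 control and 148 Lutathera patients, medians 15 and 30 months. With exponential PFS, the control hazard is ln 2 / (15 × 30.4375 / 7) = 0.01063 per week, and half that on Lutathera. Events in weeks 24–48, ignoring dropout:

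- control: 74 × (0.7749 − 0.6004) = 12.9
- Lutathera: 148 × (0.8803 − 0.7749) = 15.6
- total: 28.5

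The documents give neither the share of Week 24 scans done early nor the share of patients who miss only Week 36, so both are assumed:

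| Week 24 scan early | Miss only Week 36: 2% | 5% | 10% |
|---|---|---|---|
| 25% | 0.14 | 0.36 | 0.71 |
| 50% | 0.29 | 0.71 | 1.43 |

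Each cell is 28.5 × the two proportions. It is slightly generous, because dropout is ignored and events found before LATA + 154 days still count.

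**The case against.** The strongest reply is that 5.5 already contains the right rule. It matches the LATA to a visit and computes the limits for that visit; the threshold column and the week 21 example would have little purpose if raw dates decided; and Week 16 and Week 24 are row labels in the table, so Rules 2 and 3 can be read as naming visits. On that reading nothing is wrongly censored for in-window scans. This stands, and it rules out the stronger inference that the SAP will censor PFS events after a single missed scan. It does not remove the contradiction: the sentence introducing the rules, and all three rules, speak of when the LATA happens or occurs.

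Three other inferences also go too far:

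- **That every event after one missed scan is at risk.** Deaths and off-schedule progressions up to LATA + 154 days count under either reading.
- **That nearly half of Week 24 scans are affected.** Days 161–167 are 7 of 15 allowed days, but that is a share of the calendar, not of patients.
- **That the table errors alter censoring.** Step 6 shows that they do not.

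It is also fair to say that the actual-event supplementary analysis in SAP 2.5.6 counts events even after two or more missed scans, so it would recover these events, and that the censoring-reason table would show them by arm. Both make the problem visible; neither corrects the primary analysis.

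**Conclusion.** SAP 5.5 contradicts itself on what selects D1 and D2. Under the literal rule wording, an in-window Week 24 scan on days 161–167 followed by a missed Week 36 scan leads to censoring of any progression found at the Week 48 scan, against Table 2.5-1 row C and the 182-day limit implied by 2.5.4. It also flags an on-time Week 36 progression as following a missed scan. Under the matched-visit wording neither occurs for in-window scans.

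The expected effect is small, roughly 0.1 to 1.4 of 99 events, resting on the design medians and on assumed rates for early and missed scans. Nothing here shows a material change in the hazard ratio, power or type I error, and the documents give no scan-day data from which to judge whether the arms would differ. The point merits correction because two programmers following the same text could produce different primary PFS data. The Week 24 row is wrong on its face, but correcting it is editorial.

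**What to change.** - **Word the rules by matched visit:** Rule 1 if the LATA is matched to baseline, Rule 2 if matched to Week 16, Rule 3 if matched to Week 24 or later.
- **State the cut-off between baseline and Week 16.** The table gives N/A for baseline, so matching cannot separate Rule 1 from Rule 2 without one. The mid-point, week 8, is one option; it would be a new convention, since the footnote exempts baseline from the mid-point definition.
- **Correct the Week 24 row** to 23 / 24 / 25 / 30, after checking the two cells against the master file in case the fault arose in text conversion.
- **If the derivation is already programmed,** record which reading was used and list any patient whose status differs between the two.

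The change protects in-window scans only. A LATA at week 21 (day 147) with progression at week 48 (day 336) is 189 days apart and stays censored under the 182-day limit.

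The cost is a few lines of SAP text and one derivation. No new data are needed.
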